Number of Subjects Planned: Approximately 30 eligible subjects will be randomized and dosed such that at least 24 subjects complete all five periods. The selection of sample size is empirical. However, based on the reported approximate 10% intra-subject variability of the Reference Zyrtec®10 mg tablet, it's expected that 24 completed subjects should be adequate for evaluation of relative bioavailability and PK in this single dose, 5-period crossover study. Assuming up to a 20% dropout rate, 30 subjects will be randomized in the study.		
Study Design and Methodology: This is an open-label, single dose, randomized, five-period, crossover design study to evaluate the relative bioavailability of a single oral dose of cetirizine HCl Gummy 10 mg (Test) and cetirizine HCl oral tablets 10 mg (Zyrtec®, Reference) under fasted conditions in healthy adult male and female subjects, and the impact on the bioavailability of cetirizine HCl Gummy 10 mg when administered with food, when administered with or without water, and when chewed or swallowed whole.		

Name of Sponsor/Company: Seattle Gummy Company	Individual Study Table Referring to Part of Dossier in Which the Individual Study or Study Table is Presented:	(For National Authority Use Only)
Name of Finished Product: Ceteric™ Allergy Gummy Regular		
Name of Active Ingredient: Cetirizine HCl		

Following a screening period of up to 28 days, eligible subjects will be enrolled and randomized to receive study drug. Subjects will be confined to the Clinical Research Unit (CRU) for two overnight stays during each of the five study periods.

Eligible subjects will receive a single oral dose of one of five treatments (Treatments A, B, C, D or E) in five separate periods in a randomly assigned sequence, with each treatment separated by an approximate 5-day washout period. In each study period dosing will occur in the morning after an overnight fast of at least 10 hours.

All doses will be administered under fasted conditions except for Treatment C, when cetirizine HCl Gummy 10 mg will be administered after consumption of a high-calorie, high-fat breakfast.

All doses will be administered with approximately 240 mL of room temperature water except for Treatment D, when cetirizine HCl Gummy 10 mg dose will be administered without water.

All doses of cetirizine HCl Gummy 10 mg will be chewed before swallowing except for Treatment E, when subjects will be instructed to swallow the dose whole.

Treatment	Treatment Description

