
(cetirizine HCl Gummy 10 mg, chewed) administered with 240 mL room temperature water under fed conditions;
 
Treatment A / Treatment D
 
The relative bioavailability of the Test formulation (cetirizine HCl Gummy 10 mg, chewed) administered with 240 mL room temperature water under fasted conditions will be compared to the Test formulation (cetirizine HCl Gummy 10 mg, chewed) administered without 240 mL room temperature water under fasted conditions;
 
Treatment A / Treatment E
 
The relative bioavailability of the Test formulation (cetirizine HCl Gummy 10 mg, chewed) administered with 240 mL room temperature water under fasted conditions will be compared to the Test formulation (cetirizine HCl Gummy 10 mg, swallowed whole) administered with 240 mL room temperature water under fasted conditions.
 
For each of the comparisons, confidence intervals (CIs; 90%) will be constructed to test the two one-sided hypotheses at the $\alpha = 0.05$ level of significance for C_{max}, AUC_{0-t} and $AUC_{0-\infty}$. Log-transformed PK parameters C_{max}, AUC_{0-t} and $AUC_{0-\infty}$ will be analyzed using an analysis of variance (ANOVA) model with fixed effects for treatment and sequence, and a random effect of subject nested in sequence.
 
The arithmetic means, geometric means, and ratio of the geometric means and 90% CIs on the ratios of each comparison will be displayed.
 
Nonparametric analyses of T_{max} and $t_{1/2}$ (between Test and Reference formulations) may be performed using Wilcoxon Signed Rank Test. The corresponding 95% CI for the difference in medians will be reported using Walsh Averages and 25th and 75th percentiles of the Wilcoxon Signed Rank Statistic Test.
 
Plots of mean concentrations of plasma cetirizine versus time will be generated for each treatment group. Individual concentrations versus time graphs will also be provided.
 
Statistical tables will be generated using SAS version 9.4 or higher.
 
Adverse events will be coded using a standardized Medical Dictionary for Regulatory Activities (MedDRA), Version 22,0 or higher. Prior and concomitant medications will be coded using the World Health Organization (WHO) Drug Enhanced Dictionary (March 2019 or later). The proportion of subjects experiencing AEs will be summarized by treatment group. Tabulations will be prepared including all AEs and all AEs by relationship and severity. Adverse events resulting in early termination and events meeting regulatory criteria for seriousness will also be tabulated separately. By-subject listings of all safety data and concomitant medication use will be generated.

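### The primary ANOVA for this five-period crossover has no period term, so period differences widen the 90% CIs and, with the planned 24 completers, also shift the treatment ratios

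*Protocol*

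**What the plan says.** The Protocol, section 3 (Protocol Synopsis), under Relative Bioavailability Comparisons, gives one model for the three primary PK endpoints. They are log-transformed and "analyzed using an analysis of variance (ANOVA) model with fixed effects for treatment and sequence, and a random effect of subject nested in sequence". The 90% CIs for A/B, A/C, A/D and A/E are tied to two one-sided tests at the 0.05 level.

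Under Study Design and Methodology, each subject receives the five treatments "in five separate periods in a randomly assigned sequence, with each treatment separated by an approximate 5-day washout period". Exit procedures fall on Day 22 in Period 5. The number and type of sequences are not given.

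Under Number of Subjects Planned: "Approximately 30 eligible subjects will be randomized and dosed such that at least 24 subjects complete all five periods". The size is called empirical and is justified as adequate "based on the reported approximate 10% intra-subject variability of the Reference Zyrtec®10 mg tablet".

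No part of the protocol adds a period term.

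**The concern.** All four comparisons are within-subject contrasts. Sequence and subject-within-sequence describe differences between subjects, so neither can remove a difference between periods. Period is the term that does this, and it is the one left out.

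Two things follow if the periods differ systematically:

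- The period variation is counted as residual error. The CIs become too wide, and their actual coverage is above the nominal 90%.
- Period effects cancel from a treatment contrast only if the treatments being compared occur equally often in each period. Where they do not, part of the period difference is reported as a treatment difference.

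This model carries every primary endpoint and every bioavailability objective. It is stated in full, so it is not a detail left open for the SAP. An SAP that follows it inherits the omission, and one that adds period departs from the protocol. Adding the term after seeing the data would be a post hoc change to the primary model.

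**Working it through.** **Inputs from the protocol.** 30 randomized, at least 24 completing, up to 20% dropout, five treatments in five periods, and within-subject CV about 10%. The log-scale variance is σ² = ln(1 + 0.10²) = 0.00995.

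**Assumptions, not in the protocol.** The sequence set is a 5-sequence Latin square or a 10-sequence Williams design. The 24 completers are a random subset of the 30. The period effect is a linear drift of 5% to 20% from Period 1 to Period 5, with a first-period shift as an alternative.

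**The protocol's own figure.** 24 / (1 − 0.20) = 30, which reproduces the number randomized. No power is stated, so none can be reproduced.

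**Degrees of freedom.** 24 × 5 = 120 observations. Without period: 119 − 23 (subjects, including sequence) − 4 (treatments) = 92. With period: 92 − 4 = 88. The 95th percentile of t goes from 1.6616 to 1.6624.

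**Error inflation.** With period effects π_j and Q = Σ(π_j − mean π)², the expected residual mean square without period is approximately σ² + nQ / [4(n − 1)].

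- 10% drift: step = ln(1.10)/4 = 0.02383; Q = 10 × 0.02383² = 0.00568; added variance ≈ 24 × 0.00568 / 92 = 0.0015. Simulation gives a total of 0.01142, which is 15% above σ².
- 20% drift: step = ln(1.20)/4 = 0.04558; Q = 0.02078; added variance ≈ 24 × 0.02078 / 92 = 0.0054. Simulation gives 0.01532, which is 54% above σ².

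**90% CI half-width on the log scale**, t × √(2 × variance / 24):

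- With period: 1.6624 × √(2 × 0.00995 / 24) = 0.0479, whatever the drift.
- Without period, 10% drift: 1.6616 × √(2 × 0.01142 / 24) = 0.0513.
- Without period, 20% drift: 1.6616 × √(2 × 0.01532 / 24) = 0.0594.

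**Simulated comparison of the two models** (3000 replicates per setting, A/B contrast):

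| Drift, Period 1 to 5 | CI width, without / with period | Coverage without period |
|---|---|---|
| 0% | 0.995 | about 90% |
| 5% | 1.015 | about 90–91% |
| 10% | 1.07 | about 92% |
| 15% | 1.14 | about 93–94% |
| 20% | 1.24 | about 95% |

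With period in the model, coverage stays near 90% throughout. The 0.5% cost at zero drift comes mostly from treatment and period no longer being orthogonal; the loss of 4 df alone contributes only 1.6624/1.6616, or 0.05%.

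**Leakage into the ratio.** Without period, the shift in ln(A/B) is Σ_j (n_Aj − n_Bj) π_j / 24, where n_Aj is the number of subjects receiving A in period j. Full balance would need 24/5 = 4.8 subjects per treatment per period, which is impossible. In 20,000 draws of 24 from a balanced 30 on the Williams design, the five treatments never had identical period counts, and A and B did in 1.6% of draws.

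| Drift | Mean absolute shift in ln(A/B) | 95th percentile |
|---|---|---|
| 10% | 0.003–0.004 | 0.007–0.009 |
| 20% | 0.006–0.007 | 0.013–0.017 |

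The ranges cover the Williams design and a cyclic Latin square. If the difference is confined to the first period, the root-mean-square shift is 0.006 at 10% and 0.011 at 20%. The largest shift seen in any of the four ratios was about 0.046, at 20%. If all 30 complete on a balanced set of sequences, the leakage is exactly zero and only the error inflation remains.

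**The case against.** The strongest case on the other side is about size.

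- **The harm depends on a period effect that the protocol gives no reason to expect.** These are single doses in healthy, confined subjects at a fixed clock time with about five days between doses. At a 5% drift the CI is only 1.5% wider. This stands: the figures are conditional on the drift.
- **The main error is conservative.** Over-coverage makes similarity harder to show, so it does not by itself raise the false-positive rate. This stands for the inflation. The leakage can go either way, but it is usually 1% of the ratio or less for linear drifts up to 20%.
- **Conclusions would rarely change.** Under assumed limits of 80–125% (the protocol states none), n = 24 and CV 10%, power at a true ratio of 0.95 stays above 99.9% even with a 20% drift. At a true ratio of 0.90 it falls from about 99% to about 97–98%. This stands at a 10% CV, but that figure is reported for the Reference tablet. It is not given for the gummy chewed, swallowed whole, fed or without water.
- **Twenty-four is a floor.** A balanced 30 would have no leakage, and the protocol does not say that subjects with partial data are excluded. Both are true. Still, 24 is the number that the protocol calls adequate, and no period-balanced sequence set is stated even for 30.

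None of these points supplies the missing term or gives a reason to prefer the model without it.

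**Conclusion.** The concern holds. The stated primary model is wrong for a five-period crossover. Any period difference is put into the error term, and with 24 completers part of it also reaches the treatment ratios.

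At a 10% CV, a drift of 10% to 20% makes the A/B 90% CI about 7% to 24% wider than it should be and raises coverage to about 92% to 95%. The average shift in ln(A/B) is about 0.003 to 0.007. These figures rest on the assumed drift, sequence set and random dropout. The omission itself and the impossibility of balance at 24 do not.

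The practical effect is small to moderate and mainly conservative. It should nevertheless be corrected before analysis, because it affects every primary result, the correction costs almost nothing, and it cannot be made cleanly after the data are seen.

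**What to change.** State the model as fixed effects for sequence, period and treatment, with subject nested in sequence as the random effect. Take the four ratios and their 90% CIs from the least-squares means of that model. Make the same statement in the SAP; if the SAP already includes period, amend the protocol to agree.

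The cost is one added term and 4 error degrees of freedom (92 to 88 with 24 completers). The CI is about 0.5% wider if there is no period effect. No extra subjects or data are needed.

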A	Test: Single oral dose of cetirizine HCl Gummy 10 mg, chewed, administered with approximately 240 mL of room temperature water, under fasted conditions
B	Reference: Single oral dose of cetirizine HCl oral tablets 10 mg, administered with approximately 240 mL of room temperature water, under fasted conditions
C	Test: Single oral dose of cetirizine HCl Gummy 10 mg, chewed, administered with approximately 240 mL of room temperature water, under fed conditions
D	Test: Single oral dose of cetirizine HCl Gummy 10 mg, chewed, administered with no water, under fasted conditions
E	Test: Single oral dose of cetirizine HCl Gummy 10 mg, swallowed whole, administered with approximately 240 mL of room temperature water, under fasted conditions

In each study period, confinement to the CRU will begin the day prior to dosing during each period and continue until after collection of the 36-h pharmacokinetic (PK) post-dose sample the evening of the day following dosing. Subjects will be discharged from the study after exit procedures are completed on Day 22 in Period 5, or after Early Termination.

Following an overnight fast of at least 10 hours, subjects will receive a single oral dose of their assigned study drug with approximately 240 mL of room temperature water (except when assigned to Treatment D) at approximately 0800 hours (± 1 hour). Subjects assigned to Treatment C will consume a standardized high calorie, high fat breakfast within approximately 30 minutes prior to dosing.

During each of the five study periods, serial PK blood samples to measure plasma concentrations of cetirizine will be collected by direct venipuncture or by use of an indwelling cannula prior to dosing (up to 60 minutes prior to dosing), 10, 20 minutes post-dose and 0.5, 1, 1.5, 2, 2.5, 3, 4, 6, 8, 10, 12, 24, 36 hours post-dose. Where PK sampling time points coincide with vital sign measurements, vital signs will be collected ± 10 minutes of the scheduled time point, and PK samples will be collected at the scheduled time point.

Height and weight will be measured and body mass index (BMI) will be calculated at Screening. A full physical examination (PE) will be performed at Screening, and an abbreviated PE will be performed at the Study Exit/Early Termination Visit. Physical examinations may be repeated prior to study discharge as deemed necessary by the Investigator or in response to adverse events (AEs).

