
Pharmacokinetic and Safety Variables
 
Pharmacokinetic: Plasma concentrations of cetirizine will be measured and PK parameters, including C_{max}, T_{max}, AUC_{0-t}, $AUC_{0-\infty}$, K_{el} and $t_{1/2}$, will be determined using non-compartmental analysis methods (Phoenix WinNonlin software, version 8.1 or higher, Certara USA Inc., Princeton, NJ).
 
Safety: Safety will be based on the frequency of AEs and changes in vital signs, clinical laboratory assessments and PE findings.
 
Statistical Methods and Planned Analysis: The primary PK endpoints will be maximum plasma cetirizine concentration (C_{max}), and area under the plasma drug concentration versus time curve calculated to the last measurable observation (AUC_{0-t}) and extrapolated to infinity ($AUC_{0-\infty}$).
 
The secondary PK endpoints will be time to C_{max} (T_{max}), elimination half-life ($t_{1/2}$) and terminal elimination rate constant (K_{el}).
 
The safety and tolerability of single 10 mg oral doses of cetirizine HCl, as assessed by incidence of TEAEs, study discontinuation information, laboratory test results, vital signs and PE findings will be secondary endpoints.
 
Relative Bioavailability Comparisons: The following comparisons will be assessed:
 
Treatment A / Treatment B The relative bioavailability of the Test formulation (cetirizine HCl Gummy 10 mg, chewed) administered with 240 mL room temperature water under fasted conditions will be compared to the Reference formulation (cetirizine HCl oral tablets 10 mg) administered with 240 mL room temperature water under fasted conditions;
 
Treatment A / Treatment C The relative bioavailability of the Test formulation (cetirizine HCl Gummy 10 mg, chewed) administered with 240 mL room temperature water under fasted conditions will be compared to the Test formulation
		

Name of Sponsor/Company: Seattle Gummy Company	Individual Study Table Referring to Part of Dossier in Which the Individual Study or Study Table is Presented: Volume: Reference:	(For National Authority Use Only)
Name of Finished Product: Ceteric™ Allergy Gummy Regular		
Name of Active Ingredient: Cetirizine HCl		

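### Tmax is a secondary endpoint, but its only planned comparison covers gummy against tablet; the food, water and chewing pairs get no paired estimate of a shift in Tmax

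*Protocol*

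**What the plan says.** All references are to the Protocol, section 3 (Protocol Synopsis).

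- **Endpoints.** Under Statistical Methods and Planned Analysis, Cmax, AUC0-t and AUC0-inf are primary. Tmax is secondary: "The secondary PK endpoints will be time to C_{max} (T_{max}), elimination half-life", followed by Kel.
- **Comparisons.** Four pairs are listed: A/B, A/C, A/D and A/E. The last three serve the secondary objectives. Study Design and Methodology describes these as the impact on the gummy's bioavailability "when administered with food, when administered with or without water, and when chewed or swallowed whole".
- **Analysis made for every pair.** "For each of the comparisons, confidence intervals (CIs; 90%) will be constructed to test the two one-sided hypotheses", for Cmax, AUC0-t and AUC0-inf only.
- **Analysis of Tmax and t1/2.** The nonparametric analysis is qualified in brackets: "between Test and Reference formulations) may be performed using Wilcoxon Signed Rank Test". The next sentence promises a 95% CI for the difference in medians, built from Walsh averages and the 25th and 75th percentiles of the signed-rank statistic.
- **Labels in the treatment table.** B is "Reference: Single oral dose of cetirizine HCl oral tablets 10 mg, administered with approximately 240 mL of room temperature water, under fasted conditions". C is "Test: Single oral dose of cetirizine HCl Gummy 10 mg, chewed, administered with approximately 240 mL of room temperature water, under fed conditions". D is "Test: Single oral dose of cetirizine HCl Gummy 10 mg, chewed, administered with no water, under fasted conditions". A and E are also labelled Test.

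**The concern.** A meal, the absence of water, or swallowing the gummy whole could plausibly change when the drug is absorbed without much changing how much is absorbed. (This mechanism is a reviewer's assumption; the protocol does not state it.) Tmax is the named endpoint that addresses timing directly. Yet the bracketed restriction leaves out exactly the three pairs in which these conditions are varied.

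If one condition delayed absorption while the Cmax and AUC ratios stayed near 1, the report would have no planned figure for the size of the delay or its uncertainty. Readers would have to judge it from separate treatment summaries and plots, although every completer supplies a within-subject difference.

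**Working it through.** **1. Which pairs the wording reaches.** The treatment table labels A, C, D and E as Test and B as Reference.

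| Pair | First | Second | Test against Reference? | Cmax and AUC compared? | Tmax comparison planned? |
|---|---|---|---|---|---|
| A/B | Test | Reference | yes | yes | optional |
| A/C (food) | Test | Test | no | yes | no |
| A/D (water) | Test | Test | no | yes | no |
| A/E (chewing) | Test | Test | no | yes | no |

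The count is 1 of 4 listed comparisons and 0 of the 3 for the secondary objectives. The descriptions of A/C, A/D and A/E also call both sides the Test formulation.

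**2. Are the paired data there?** Yes. PK samples are taken on the same schedule in all five periods, half-hourly from 0.5 to 3 h. The synopsis plans at least 24 completers. Its figure of 30 randomized reproduces as 24 / (1 - 0.20) = 30, and nothing in this point alters it.

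**3. Can timing shift while the compared ratios stay near 1?** This is an illustration on assumptions not in the protocol: a one-compartment model with first-order absorption, half-life 6 to 10 h, and absorption rate constant ka halved from 3 to 1.5 per hour.

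- ke = ln 2 / half-life = 0.1155 per hour (6 h) or 0.0693 per hour (10 h).
- Tmax = ln(ka/ke) / (ka - ke).
  - Half-life 6 h: 1.13 h becomes 1.85 h, a shift of 0.72 h.
  - Half-life 10 h: 1.29 h becomes 2.15 h, a shift of 0.86 h.
- Cmax is proportional to exp(-ke x Tmax), so the slow/fast ratio is exp(-ke x shift).
  - Half-life 6 h: exp(-0.1155 x 0.723) = 0.92.
  - Half-life 10 h: exp(-0.0693 x 0.863) = 0.94.
- AUC0-36 is proportional to [ka/(ka - ke)] x [(1 - exp(-36 ke))/ke - (1 - exp(-36 ka))/ka].
  - Half-life 6 h: 8.510 / 8.516 = 0.999.
  - Half-life 10 h: 13.180 / 13.209 = 0.998.

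So Tmax moves by 0.7 to 0.9 h, more than one half-hour sampling step, while Cmax falls by 6 to 8% and AUC hardly moves. Cmax does register slower absorption, but weakly. A pure lag is the limiting case: true Tmax shifts by the whole lag, and true Cmax and AUC0-inf do not change.

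**4. Can the planned interval simply be repeated?** No. Limits at the 25th and 75th percentiles enclose the central 75 - 25 = 50% of the signed-rank distribution. A 95% interval needs the 2.5th and 97.5th: 97.5 - 2.5 = 95%. Repeating the interval as written for three more pairs would repeat the error.

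**The case against.** The strongest case against has four parts.

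- **Rate of absorption is not ignored.** Cmax is a primary endpoint and is tested for all four pairs. This stands, and it narrows the point. A reader might infer that a delay would pass unnoticed whenever AUC is unchanged, but the protocol does not support that. Only a delay that also leaves Cmax nearly unchanged lacks a planned comparison.
- **Timing information will exist.** A reader might also infer that C, D and E have no Tmax estimate at all. They will have one: Tmax is to be determined without limit to particular treatments, and mean plots by treatment and individual plots are planned. What is absent is the paired contrast with an interval.
- **No objective is left unanswered.** The objectives speak of relative bioavailability and do not name Tmax, and the primary PK endpoints address each of them. This stands. The gap lies in one secondary endpoint.
- **The sentence is permissive, and such tests are often left to the SAP.** This stands in part. The word *may* makes even the A/B comparison optional, and nothing forbids adding pairs. But the protocol is not silent: it states a scope, and that scope excludes three of its own four comparisons. Reading C, D or E as the reference in its pair does not rescue the wording, because the restriction is to formulations and all three are the same formulation as A.

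The argument does not carry over to t1/2. The timing rationale concerns absorption, and nothing in the protocol suggests that food, water or chewing calls for a half-life comparison.

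**Conclusion.** The point holds in a limited form and is a minor, free improvement. The only comparison planned for Tmax is optional and, as worded, applies to A/B alone, so the three pairs behind the secondary objectives have no planned paired estimate or interval for a Tmax shift.

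The conclusion about scope rests only on the protocol's labels and the bracketed restriction. The claim that Cmax and AUC can miss a delay rests on the model assumptions above. These show that it is possible; they do not show that the gummy behaves this way. The primary A/B conclusion, the Cmax and AUC comparisons, the sample size and the data collected are all unaffected.

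**What to change.** In Statistical Methods and Planned Analysis, replace the bracketed restriction and the optional verb so that the sentence says: *nonparametric analysis of Tmax will be performed for each of the comparisons A/B, A/C, A/D and A/E using the Wilcoxon signed rank test.*

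In the sentence that follows, specify the Hodges-Lehmann median paired difference (the median of the Walsh averages) with a 95% CI based on the 2.5th and 97.5th percentiles of the signed-rank distribution, not the 25th and 75th.

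The t1/2 analysis may stay as it is apart from the percentile correction; extending it to the other pairs is optional.

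The cost is two edited sentences and three further runs of an analysis already described, on data already collected.

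### The interval for Tmax and t1/2 is labelled 95%, but the percentiles that set its limits give about 50% coverage for untied data

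*Protocol*

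**What the plan says.** Protocol Section 3 (Protocol Synopsis), under Statistical Methods and Planned Analysis, describes an optional nonparametric comparison of Tmax and t1/2: "between Test and Reference formulations) may be performed using Wilcoxon Signed Rank Test". It then fixes the interval to go with it, a "95% CI for the difference in medians will be reported using Walsh Averages and 25th and 75th percentiles of the Wilcoxon Signed Rank" statistic. Both variables are listed as secondary PK endpoints in the same section.

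Nothing else in the protocol redefines this level or these percentiles. The 90% intervals described nearby concern only Cmax, AUC0-t and AUC0-inf.

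**The concern.** In the Walsh-average (Hodges-Lehmann) method, percentiles of the signed-rank null distribution decide which ordered Walsh averages become the confidence limits. A two-sided 95% interval leaves 2.5% in each tail. The stated percentiles leave 25% in each tail, which describes roughly a 50% interval.

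If a programmer follows the percentiles, the reported 95% interval for t1/2 would exclude zero in about half of all studies with no true formulation difference. For Tmax the error could be anywhere from none to large, depending on how variable Tmax is.

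**Working it through.** **Inputs from the protocol**
- Nominal level: 95%. Percentiles for the limits: 25th and 75th of the signed-rank statistic (Statistical Methods and Planned Analysis).
- Number of pairs: between 24 ("at least 24 subjects complete all five periods") and 30 ("Assuming up to a 20% dropout rate, 30 subjects will be randomized in the study"). The two figures agree: 24 / (1 − 0.20) = 30.
- Sampling times, which are the source of ties in Tmax: "10, 20 minutes post-dose and 0.5, 1, 1.5, 2, 2.5, 3, 4, 6, 8, 10, 12, 24, 36 hours post-dose" (Study Design and Methodology).

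**Formula.** With n paired differences there are M = n(n+1)/2 Walsh averages, ordered W(1) to W(M). For continuous symmetric differences, the interval from W(k) to W(M+1−k) has exact coverage 1 − 2·P(T ≤ k−1), where T is the signed-rank statistic under the null. Here k is the smallest value with P(T ≤ k) at or above 0.25 (rule as written) or 0.025 (rule that matches the label). The distribution of T was computed exactly.

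**Exact results, untied data**

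| n | M | Percentiles | Limits | P(T ≤ k−1) | Coverage |
|---|---|---|---|---|---|
| 24 | 300 | 25th/75th | W(126), W(175) | 0.2454 | 50.9% |
| 24 | 300 | 2.5th/97.5th | W(82), W(219) | 0.0245 | 95.1% |
| 30 | 465 | 25th/75th | W(199), W(267) | 0.2449 | 51.0% |
| 30 | 465 | 2.5th/97.5th | W(138), W(328) | 0.0249 | 95.0% |

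The stated 95% is therefore not reproduced by the stated percentiles.

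- **Rank span.** At n=24 the limits lie 175 − 126 = 49 ranks apart instead of 219 − 82 = 137. At n=30 they lie 68 apart instead of 190. The ratio is 0.36 in both cases.
- **Indexing convention.** Moving both limits in by one rank gives 49.1% (n=24) and 49.7% (n=30). Taking the 75th percentile of T literally as the upper rank (174 at n=24) gives 50.0%; the same literal reading of the 97.5th (218) gives 94.9%. The result does not depend on the convention.
- **Another reading.** If the sentence meant the quartiles of the Walsh averages themselves, k is M/4 rounded down (75 and 116) and coverage is 97.1% and 98.5%. That does not match 95% either.
- **Simulation check, untied.** With 20,000 runs per n, lognormal values and an assumed CV of 15%, zero was falsely excluded in 49.3% (n=24) and 48.8% (n=30) of runs as written, against 5.1% and 4.9% with the 2.5th/97.5th percentiles. The mean width ratio was 0.34.

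**Tmax, illustrative only.** The protocol gives no Tmax distribution. Assumptions: no true difference; independent lognormal values with median 0.75, 1.0 or 1.25 h, rounded to the nearest post-dose sampling time; n=24 or 30; all differences kept, including zeros (11 to 83% of them); 6,000 runs per setting. Zero was falsely excluded under the rule as written in:

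| Assumed CV | False exclusion of zero |
|---|---|
| 15% | 0 to 2.8% |
| 30% | 2.7 to 7.5% |
| 50% | 12 to 18% |
| 70% | 21 to 25% |
| 100% | 30 to 33% |
| 150% | 35 to 39% |

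With the 2.5th/97.5th percentiles the range over all these settings was 0 to 3.5%.

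**The case against.** The strongest reply is that this is a slip with little consequence. The sentence names the method and the 95% level, and those two alone fix the interval; exact routines normally take the level, not percentiles, as input. The analysis is optional, compares only Test with Reference, and carries no decision rule. The signed-rank p-value would remain valid and would visibly disagree with a 50% interval, so the error could be noticed. All of this stands, and it is why the point is minor. It does not make the sentence right: once the analysis is run, the text says how the interval will be built. A decimal point lost in text extraction is not an explanation either, because 97.5 would then read 975, not 75.

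The second objection is to the Tmax figures, and it partly stands.
- **Independence.** The two values per subject were drawn independently, although this is a crossover. With an assumed within-subject log correlation of 0.5 at n=24, false exclusion falls to roughly 1.4 to 3% at CV 30% and 7 to 11% at CV 50%, and to 23 to 29% at CV 100%.
- **Zero differences.** If they are dropped, as the classical signed-rank test does, false exclusion rises to about 9 to 12% at CV 30% and 21 to 24% at CV 50%. At CV 15% and median 1 h so few non-zero pairs remain that even the 2.5th/97.5th rule excludes zero in about a fifth of runs.

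The Tmax ranges therefore show only that coverage is uncertain. The exact result for untied data needs none of these assumptions.

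**Conclusion.** The concern holds and is minor. The stated level and the stated percentiles cannot both be right. For untied differences such as t1/2, the rule as written covers about 50% (50.9% at n=24, 51.0% at n=30). This is exact and rests only on continuous, symmetric differences and the protocol's own sample sizes. For Tmax the claim is weaker: 95% is not assured, and the size of any shortfall depends on Tmax variability, within-subject correlation and the handling of zero differences, none of which the protocol gives. At low variability, with zeros kept, there may be no under-coverage. The signed-rank test itself and the primary Cmax and AUC comparisons are not affected.

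**What to change.** In the nonparametric sentence of Statistical Methods and Planned Analysis, replace the 25th and 75th percentiles with the 2.5th and 97.5th percentiles of the Wilcoxon signed-rank distribution. At n=24 this selects ordered Walsh averages 82 and 219 of 300, with exact coverage of 95.1% for untied data. For Tmax the interval is conservative when zero differences are kept (zero covered in at least 96.5% of runs in the independent-draw simulations above). That assurance does not extend to dropping zeros when Tmax varies very little, so the handling of zeros should be settled when the interval is programmed.

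The cost is two numbers in one sentence, changed before analysis. The reported interval becomes about three times wider for untied data (1 / 0.34 ≈ 2.9), and wider for Tmax by an amount that depends on the ties. Sample size, data collection and the primary analysis stay as they are.
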